In 2010, as part of our technical support to the implementation of PMTCT in Kinshasa, we developed and supported the implementation of a mother-infant register in 105 MCH clinics to monitor PMTCT care provided in these clinics. The registry was modeled after the WHO's Three Interlinked Patient Monitoring Systems for HIV Care/ART, MCH/PMTCT (including malaria prevention during pregnancy), and TB/HIV: Standardized Minimum Data Set and Illustrative Tools. The register is used to track important HIV care events among HIV-infected pregnant women and subsequently their HIV-exposed infants, from the first contact with the ANC clinic through delivery and the effective linkage of the mother-infant pairs to HIV care and treatment (C&T) services. The following key information is documented in the register: a maternity code that is used to link mother and infant, address and telephone number, gestational age at HIV diagnosis, date of birth, date of reference to HIV C&T if any, date of first visit at C&T and a code number assigned to the mother at C&T, and other information necessary to calculate PEPFAR's PMTCT indicators. For mother-infant pairs who still need to integrate HIV C&T services after delivery, information on infant feeding practices, cotrimoxazole prophylaxis at subsequent visits, date of first sample collection for early infant diagnosis at six weeks and the result, a second sample collection and result at nine months, and eventually a serological test at 18 months for all infants with HIV-negative PCR results is also documented. For real time use of information in the register, nurses who supervised the implementation of PMTCT technical assistance were each equipped with a laptop including the electronic version of the register (in the open-source software Epi-info) and at each clinic visit, they extracted information for the register into the electronic database and returned the updated database to the central team. The same scheme was used for monitoring in our study on conditional cash transfers with a group of nurses who successfully visited on a regular basis the 90 MCH clinics that were enrolled to extract the data in the electronic database. Because of its success, the register has been adapted by the PNLS for the monitoring of Option B+. We will rely on the register to obtain information on the outcomes with study nurses visiting the clinics on regular basis to extract key information for the study into the database.

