Table 1. Outcomes and definitions

Outcomes	Definition
Primary	
loss-to-follow-up	Proportion of HIV+ pregnant women initiated on ART for whom the whereabouts is unknown
Timely infant HIV diagnosis	Proportion of HIV-exposed infant with an appropriate HIV test result
Secondary	
Timely ART initiation	Proportion of HIV-infected participants (mother and infant) initiated on ART within two weeks of diagnosis
Retention in care	Proportion of participants who are known to be receiving HIV care
Non-adherence to scheduled visits	Proportion of participants whose whereabouts is unknown or who are in care but have missed at least one scheduled visit over the evaluation period
Virological suppression	Proportion of participants with undetectable viral load
MTCT rates	Proportion of infants born to participating women who tested positive for HIV
Survival	Proportion of participants known to be alive

For key laboratory tests, CD4 count is generally available free of charge at decentralized locations (over 70 MCH clinics) in Kinshasa and is done at HIV diagnosis and every six months. Viral load measurement is accessible at the national reference laboratory in downtown Kinshasa at a subsidized cost of \$25 or at private facilities (Dream, Doctors Without Borders—MSF) at higher cost per test and is recommended for every patient on ART at least once a year. We have budgeted this to ensure that each participant has at least one viral load measurement at enrollment and every year thereafter during this study.

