Healthcare system delivery characteristics and measurements: The Facility Audit of Service Quality (FASQ) will be adapted to assess the key organization characteristics of HIV care (including lifelong ART) delivery in participating MCH clinics. FASQ is a relatively low cost approach developed, by MEASURE Evaluation, for district level monitoring or service availability and quality.⁶⁸ It provides information on the type of services; status and functionality of infrastructure, equipment and quality of care. The key areas covered include: 1) the range of services offered (HIV testing and counseling, lifelong ART, laboratory), staffing and staff qualifications, operating hours, community linkages, selected administrative and quality control procedures; 2) Facility infrastructure (privacy/capacity, laboratory, delivery, well-child clinics); 3) Readiness to provide quality care in six areas: family planning; STI management; antenatal care; maternal/delivery care and post abortion care; child health/welfare; and HIV prevention, treatment, and care; and the digital maps of facilities and services available. This survey of health facilities participating in the study will be repeated every year thereafter (to monitor change). In each facility, individual-level patient characteristics including: socio-demographic and economic characteristics, beliefs about the health services (cost, quality), cognitive factors (knowledge about HIV and ART, perceived susceptibility and perceived benefit of early ART, perceived self-efficacy for adherence, perceived need for ART and other HIV services), psychological factors (e.g. depression, fear of stigma), social factors (social support – friends, family, male partner involvement in MCH care, intimate partner violence), accessibility to the clinics (distance, transportation, waiting time), and evaluated health status (WHO stage, CD4 count) will also be collected through face to face interviews at enrollment (within one month of ANC registration), after delivery (2-3 days in postpartum ward), at 6 weeks (6 weeks post-partum visit), at 24 weeks (end of exclusive breastfeeding period), and every six months thereafter through the end of all breastfeeding exposure at 24 months. Data on evaluated health status will come from mother-infant pair register. We will use the same research nurses who successfully interviewed and followed 991 mother-infant pairs in our breastfeeding study, at delivery, 1 week, and monthly thereafter and in our just completed conditional cash transfer study.^{16,33}

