gaps in the service delivery. The team will develop a priority action plan to address the main gaps and agree on a set of key indicators representing critical points in the PMTCT cascade that will be used to monitor the changes resulting from the implementation of the action plan. Thereafter, the health district QI team and a study team member will visit each clinic at least once a month to supervise and support the implementation of the action plan. Every quarter, using data from the monitoring system (Aim 1), the study team working with the provincial coordination of the National AIDS Program (cPNLS) will generate a quarterly report including a color-coded dashboard for tracking changes using the 'traffic light' approach. An indicator will score green when the target has been achieved, yellow/amber when there is a progress from the baseline value without reaching the target, and red when there is no progress or downward movement. Figure 6 outlines the cascade that was followed in South Africa and highlights the indicators used at critical points in the cascade to support tracking progress and identification of gaps in service delivery.¹⁴ A similar cascade will be created with indicators agree upon with the QI teams. The report will be generated for each participating clinics in the intervention group and shared with the cPNLS, the QI teams, and the management of the clinic. QI teams will be brought together to review these indicators, share experience, identify remaining gaps in the service delivery, and develop a new priority action plan for the next quarter.

Statistical Analysis –Aim 1: The primary outcomes for this aim are loss to follow-up and MTCT over the first 24 months of follow-up. Since the characteristics of interest in this aim may vary with time and a substantial proportion of participants may drop out prior to study conclusion or MTCT, both outcomes will be modeled using a proportional odds model for discrete time survival data.⁶⁹ At each follow-up time, the proportional odds model assumes that the log-odds that an event (loss to follow-up or MTCT) has occurred by that time point is a linear function of a time-dependent intercept plus covariates, some of which are time-varying. The model also assumes that the odds ratio comparing two different levels of a covariate is constant over time (i.e., proportional odds).

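### Loss to follow-up, retention and infant testing are read from the clinic register, while only intervention clinics are supervised at least monthly and scored quarterly, so better recording can be mistaken for better care.

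*Combined protocol and SAP*

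**What the plan says.** Section III.C (Measurement / Instrumentation) names the mother-infant register as the outcome source: "We will rely on the register to obtain information on the outcomes with study nurses visiting the clinics on regular basis". Table 1 defines the outcomes at issue:

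- Loss to follow-up (primary): "Proportion of HIV+ pregnant women initiated on ART for whom the whereabouts is unknown".
- Timely infant HIV diagnosis (primary): "Proportion of HIV-exposed infant with an appropriate HIV test result".
- Retention in care (secondary): "Proportion of participants who are known to be receiving HIV care".

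In section III.D (Intervention – CQI interventions), the district QI team and a study team member are to "visit each clinic at least once a month to supervise and support the implementation of the action plan". Each quarter the study team and the provincial AIDS programme turn data from the Aim 1 monitoring system into a green, amber or red dashboard. On who receives it, the protocol says: "The report will be generated for each participating clinics in the intervention group". No comparable supervision or feedback is described for control clinics.

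Three provisions bear on the risk and are not specific to an arm. Section III.A strengthens monitoring in the MCH clinics in Phase I, before randomization. Section III.C schedules research interviews in each facility at enrollment, after delivery, at 6 and 24 weeks, and "every six months thereafter through the end of all breastfeeding exposure at 24 months". It also budgets a viral load for every participant at enrollment and yearly. Neither the interviews nor the viral load dates are named as a source for loss to follow-up or retention.

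**The concern.** All three definitions turn on what is on record. A woman who attended but whose visit was not entered looks the same as a woman who was lost. An infant whose result was not entered looks the same as one never tested. Supervision and scored cascade indicators give intervention clinics a reason, and help, to close such gaps. Some indicators could improve through fuller recording alone.

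Objective 2 is about retention and virological suppression, not documentation, and section II wants the result to support scale-up. If part of an apparent gain in retention is a gain in recording, the effect of CQI on care is overstated. The methods listed for Aim 2 (intention to treat, adjusted chi-square, logistic regression for baseline imbalance, GEE for clustering) do not correct outcome misclassification that differs by arm. The documents describe no tracing of women classed as lost, no blinded or independent ascertainment, no register audit by arm, and no sensitivity analysis for differential recording.

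**Working it through.** **The plan's own figures** (section III.B, Sample size and Justification)

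- Events: (1 + 2 + 7 + 5) predictors × 7 = 105.
- Loss by 24 months: 1 − 0.8 × 0.95 × 0.95 = 1 − 0.722 = 0.278. Then 105 / 0.278 = 377.7, so 378 participants, as stated.
- MTCT: 105 / 0.05 = 2,100, and 2,100 / 0.722 = 2,908.6, so 2,909, as stated.

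These figures reproduce. None of them gives the size of a recording bias, so the rest is an illustration.

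**False difference**

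Take 27.8% as the *recorded* loss in control clinics. It cannot be the true loss, because recording can correct only women who were misclassified. Let true retention be equal in both arms, and let better recording in CQI clinics reclassify a share f of recorded loss. The false difference is 0.278 × f:

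- f = 10%: 2.8 points (27.8% against 25.0%).
- f = 20%: 5.6 points (27.8% against 22.2%).
- f = 30%: 8.3 points (27.8% against 19.5%).

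**What the trial could detect**

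From the documents: 2,909 women and 35 districts, so 2,909 / 35 = 83.1 per district. Assumed: equal arms (1,454.5 each), two-sided alpha 0.05, 80% power, and the ICC. The design effect is 1 + (83.1 − 1) × ICC, and effective n per arm is 1,454.5 divided by it. Power = Φ[(|p1 − p2| − 1.96 × SE0) / SE1], where SE0 is the pooled and SE1 the unpooled standard error. The last three columns give the chance of a significant false benefit.

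| ICC (assumed) | Design effect | Effective n per arm | Detectable difference from 27.8% | f = 10% | f = 20% | f = 30% |
|---|---|---|---|---|---|---|
| 0.01 | 1.82 | 799 | about 6.0 points | 24% | 73% | 98% |
| 0.02 | 2.64 | 550 | about 7.2 points | 18% | 57% | 90% |
| 0.05 | 5.11 | 285 | about 9.8 points | 11% | 33% | 65% |

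At ICC 0.01 to 0.02 the false difference falls below the detectable difference for f = 10% and 20%, and above it for f = 30%. At ICC 0.05 all three fall below it. A bias below the detectable difference still raises the chance of a false positive above its nominal level and inflates the estimated effect.

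**The case against.** Much can be said for the plan.

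- **Monthly visits and the dashboard.** The monthly visits supervise the action plan; indicators are scored quarterly. That the dashboard uses the register is an inference from two sections, though a strong one. Both points stand.
- **Control clinics.** A reader might infer that they are extracted less often, or that extraction nurses also make the CQI visits. The documents say neither. One extraction scheme is described for the clinics in general, and research interviews take place in every facility. The gap is that equal frequency and separate staff are not stated.
- **Phase I.** Strengthening the monitoring system before randomization leaves less room for a later difference. It does not prevent one that CQI creates afterwards.
- **Less exposed outcomes.** A reader might infer that a positive result could never be told apart from better paperwork. That goes too far. Yearly viral load depends much less on the register, and better loss to follow-up with flat suppression would be informative. Recording cannot create an infant test result, although it can bring an existing one into view.
- **Direction.** A reader might infer bias towards CQI on every register outcome. For missed visits this is not established, since fuller records could reveal more of them.
- **Better recording as part of CQI.** It may be, but it is not what Objective 2 sets out to measure.
- **Interviews as a remedy.** Some are tied to clinic attendance, and an outcome built on them alone would drift towards study participation. This argues for using them beside the register, not in its place.

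**Conclusion.** The concern holds as a risk of differential ascertainment arising after randomization. As written, the plan lets CQI change the completeness of the outcome record in one arm, with no arm-neutral check described. The likely direction favours CQI for loss to follow-up, retention and recorded infant testing; it is unclear for missed visits, and virological suppression is less exposed. Phase I strengthening reduces the risk without removing it.

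The documents give no basis for the size. A false difference of 2.8 to 8.3 points follows only if 10% to 30% of recorded loss is reclassified in CQI clinics, and neither those shares nor the ICCs have a source in the plan. The illustration shows that a moderate recording effect could be comparable with the effect the trial can detect at low ICC. It does not show that such an effect will occur.

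**What to change.** This is a cheap improvement.

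1. Keep the whereabouts-unknown definition. Determine loss to follow-up and retention by one fixed rule, applied identically in both arms, from the register, the dated research interviews and the viral load dates. Evidence from any of these sources counts as known.
2. State one extraction schedule for both arms, and keep extraction separate from CQI visits. This also protects infant diagnosis, which would still come from the register.
3. Report agreement between register status and interview or viral load evidence, by arm.
4. Add a sensitivity analysis of loss to follow-up and retention based on the study-collected contacts alone.

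The cost is protocol wording plus some extra linkage and analysis. The interviews and viral loads are already planned, so no new staff or procedures are needed. Because interviews are partly tied to clinic attendance, the change reduces differential recording but does not eliminate it.

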Sampling strategy: According to the National AIDS Program, there are a total of 295 MCH clinics in Kinshasa currently providing PMTCT services. To inform selection, study staff will obtain information on factors that might affect the quality of care provided in each facility including: the type of management, location (health district), number of deliveries, number and type of personnel, and onsite HIV pediatric care. This information will be used to stratify clinics. Within each stratum, a random sample of facilities will be taken within each of the 35 health districts in Kinshasa. This selection scheme is adopted to ensure, for example, that health care facilities at the center of the city, which might have lower patient volumes and more patients with higher socio-economic status than facilities in peri-urban areas, are included in the final sample to ensure that the sampled clinics are representative of all clinics of similar size across the province. Clinics will be excluded if less than 500 pregnant women (less than 5 HIV-infected pregnant women) registered for antenatal care (ANC) in the clinic in 2015. All women diagnosed with HIV during pregnancy or breastfeeding in the participating MCH clinics and initiated on ART during the enrollment period and their HIV-exposed infants will be eligible for the study.

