Sample size and Justification: The traditional rule of thumb for sample size in logistic and Cox regression is ten events per predictor.⁷¹⁻⁷³ However, more recent simulation studies have revealed that serious problems aren't experienced until the number drops below five events per predictor.⁷⁴ Given the close association between logistic, Cox, and proportional odds regression models, these studies should provide a reasonable benchmark for sample size determination for our study. Thus, we adopted a rule of seven events per predictor in determining an appropriate sample size. Assuming that 1 contextual-level factor, 2 clinic-level factors, and seven patient-level factors (one socioeconomic, one cognitive, one psychological, one social, one related to accessibility to clinics, and one related to health status) will be significant at the 0.20 level in bivariate proportional odds models and that we'll need five additional terms due to polynomial trends or predictor-by-time interaction effects, our initial models for backward selection will require 105 events. We anticipate that 20% will be lost to follow-up in the first six weeks and 5% will be lost each year thereafter. Thus, for our loss to follow-up model we only require 378 participants.

However, we expect a cumulative MTCT rate of 5% by 24 months that suggests we will need 2,100 participants for this analysis assuming complete follow-up. Accounting for the expected drop-out, we will need to recruit $2100/(0.8*0.95*0.95) = 2,909$ participants. Assuming an average of 10 HIV diagnoses per year at eligible clinics, we will need to enroll in about 105 MCH clinics (3 per districts) in the first three years of the study.

C. Measurement / Instrumentation

Outcomes and measurement: Key programmatic outcomes that will be considered include: loss-to-follow-up (the proportion of HIV+ pregnant women initiated on ART for whom the whereabouts is unknown), retention in care (proportion of participants who are known to be receiving care), non-adherence to scheduled visits (proportion of participants whose whereabouts is unknown or who are in care but have missed at least one scheduled visit over the evaluation period), virological suppression (undetectable viral load), and MTCT rates (proportion of infants born to participating women who are tested positive for HIV).

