In addition to Mother-infant pair, selected health staff of participating clinic will also be interviewed to collect information clinic characteristics. No personal data will be collected from those interview and any potential risk associated with completing the interview is minimal for the participants.

Potential risks

The only potential risk is the potential for confidentiality breach as a third person or group of person (study staff) will be informed of the HIV status of participants. However, they will be appropriately trained and regularly supervised to limit this possibility.

To protect from potential breach of confidentiality, all electronic data will be stored on encrypted Iron Drives using only a code to link them to identification information in the register. The link data will be transferred to a secured server (existing) at Albert Einstein College of Medicine using secured FTP channel.

Data management Plan

Data from our study will be stored on a secured server at Albert Einstein College of Medicine. Blood specimen and placental biopsies will be stored in refrigerators (-20°C or – 80°C) at the Kinshasa School of Public Health and be available for studies by other investigators with relevant research questions and appropriate approvals (from the KSPH and the OSU IRBs).

The proposed research will include data from approximately 3000 HIV-infected mothers and their HIV exposed infants. The final dataset will include self-reported demographic and behavioral data from interviews with the subjects, clinical and laboratory data from mother-infant pair registry, blood specimens from the mother and infant and placental biopsies. A specimen collection sheet is added in the annex below. We will be collecting identifying information, including birth date, place and date of delivery. Even though the final dataset will be stripped of identifiers, we believe that there remains the possibility of deductive disclosure of subjects with unusual characteristics. Thus, when sharing, we will make the data and associated documentation available to users only under a data-sharing agreement that provides for: (1) a commitment to using the data only for research purposes and not to identify any individual participant; (2) a commitment to securing the data using appropriate computer technology; and (3) a commitment to destroying or returning the data after analyses are completed and results publish.

Informed consent

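### Table 1 defines timely ART initiation as one proportion over mothers and infants; on the plan's own figures infected infants are under 5% of it, so their result cannot be seen

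*Combined protocol and SAP*

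**What the plan says.** Section III.C, Table 1, lists timely ART initiation as a secondary outcome and defines it as "Proportion of HIV-infected participants (mother and infant) initiated on ART within two weeks of diagnosis". No other row of the table concerns the start of treatment. The list of key programmatic outcomes in the text of Section III.C omits this outcome, so it does not clarify the definition.

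The Aim 2 analysis (Section III.D) compares outcome frequencies between arms by an adjusted chi-square test, with GEE for district and clinic clustering. It mentions no separate analysis of mothers and infants.

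Two Table 1 outcomes belong to infants alone: timely infant HIV diagnosis (primary) and MTCT rates (secondary). Neither covers ART initiation in infants who test positive.

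The Survival row reads "Proportion of participants known to be alive" and does not say whose survival is meant. Other parts of the protocol point both ways:

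- The sample-size text uses 'participants' for the recruited women, and the MTCT row speaks of infants born to participating women.
- The sampling strategy says that the women and "their HIV-exposed infants will be eligible for the study", and the informed consent section refers to the infant's participation.

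**The concern.** Mothers and infected infants reach an HIV diagnosis at different times and by different routes, and there are far more mothers. In a pooled proportion the mothers decide the result. The intervention could greatly improve treatment of infected infants, or fail them entirely, and the planned comparison would barely register it.

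The two denominators also differ in kind. The eligibility text admits women who have started ART, so the maternal part measures timeliness among starters. Infants enter once diagnosed, whether or not they start. Finally, the number of infants in the pool depends on infant testing, which is a primary outcome that the intervention is meant to raise. The mix of the two groups can therefore differ between arms.

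**Working it through.** **Inputs** (Section III.B, sample size)

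- Events required: "our initial models for backward selection will require 105 events".
- MTCT: "we expect a cumulative MTCT rate of 5% by 24 months that suggests we will need 2,100 participants for this analysis assuming complete follow-up".
- Drop-out: "We anticipate that 20% will be lost to follow-up in the first six weeks and 5% will be lost each year thereafter".

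**1. Reproduce the plan's figures.** (1 + 2 + 7 + 5) terms × 7 events = 105 events. 105/0.05 = 2,100. 2,100/(0.8 × 0.95 × 0.95) = 2,908.6, rounded up to 2,909. All agree with the protocol.

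**2. Number of infected infants.** 5% of the 2,100 pairs with complete follow-up is 105. 5% of all 2,909 is 145.

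**3. Infant share of the pooled denominator** = infants/(mothers + infants).

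| Mothers | Infected infants | Infant share |
|---|---|---|
| 2,909 recruited | 105 | 105/3,014 = 3.5% |
| 2,909 recruited | 145 | 145/3,054 = 4.7% |
| 2,100 followed | 105 | 105/2,205 = 4.8% |

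The first line sets recruited mothers against infections among followed pairs. The other two use one basis throughout. With an MTCT rate m on one basis the share is m/(1 + m): 2.0% at m = 2% and 13.0% at m = 15% (assumed range). All these shares count every infected infant as diagnosed; incomplete testing would lower them.

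**4. Largest possible movement.** The pooled change equals the infant share times the change in infants. A change from 0% to 100% moves the pooled figure by 3.5 to 4.8 points. A change from 40% to 80% (assumed) moves it by 0.035 × 40 = 1.4 points at the lowest share.

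**5. Illustration of detectability.** Assumed: equal arms of 1,454 mothers and 52 infected infants, 90% timely in mothers in both arms, 30% against 80% in infants, two-sided alpha 0.05, no clustering.

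- Pooled, control: (1,454 × 0.90 + 52 × 0.30)/1,506 = 87.9%.
- Pooled, intervention: (1,454 × 0.90 + 52 × 0.80)/1,506 = 89.7%.
- Power is about 32% for the pooled comparison and over 99% in infants alone. Allowing for clustering would lower both.

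**6. Illustration of a shift in mix.** Assumed: 90% timely in mothers and 40% in infants in both arms, with 21 diagnosed infants in one arm (40% of 52) and 42 in the other (80%).

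- 21 infants: (1,308.6 + 8.4)/1,475 = 89.3%.
- 42 infants: (1,308.6 + 16.8)/1,496 = 88.6%.

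The pooled figure falls by 0.7 points in the arm that tests better, although timeliness is the same in each group.

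**7. Size of a separate infant row.** 105/2 to 145/2 is about 52 to 72 per arm if split equally. 105 infants over 35 districts is 3 per district.

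**The case against.** The words in brackets may be shorthand for 'in the mother and in the infant, each', and nothing in the Aim 2 text forbids reporting by group. That may be the intention, but the row states one proportion and no separate reporting is promised anywhere. If two results are meant, saying so costs nothing.

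The outcome is secondary, and infants are not ignored: timely infant diagnosis is a primary outcome and MTCT is a separate secondary one. This stands, and it limits the weight of the point. It does not fill the gap, because neither outcome shows infant ART initiation.

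A split does not cure everything. It removes the shift in mix shown in step 6, but the infant denominator is still the infants diagnosed, so the infants compared may differ between arms because testing differs. With about 105 infants the row will be largely descriptive. Both objections stand. They limit precision and interpretation; they do not justify pooling.

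A reader might infer that Survival is pooled too, so that with about one infant per mother an infant-only effect would be halved. The documents do not establish this. The Survival row does not mention infants, and the one row that adds them in brackets suggests that the bare word need not include them. The Aim 2 text describes intent-to-treat in terms of women. Against that stand the eligibility and consent texts, and the data management plan, which describes "approximately 3000 HIV-infected mothers and their HIV exposed infants". If infants are included they are about half of that denominator; if not, they are absent. Under neither reading is it nearly all mothers.

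**Conclusion.** The point holds for timely ART initiation. As written, infected infants make up about 3.5 to 4.8% of the denominator, and no change in infants, however large, can move the outcome by as much as 5 points. This rests on the plan's 5% MTCT and its recruitment figures, with all infected infants counted as diagnosed. The timeliness rates in the illustrations are assumed and serve only to show scale. The defect concerns one secondary outcome and should be corrected; it does not touch the primary outcomes.

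For Survival, the documents support only a narrower statement: the unit is undefined, since 'participants' may mean the women or the women and their infants. The same holds for Retention in care, Non-adherence to scheduled visits and Virological suppression.

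**What to change.** 1. Replace the timely ART row in Table 1 with two outcomes: timely ART initiation in mothers, and timely ART initiation in infants diagnosed HIV-positive. Give each its own denominator.
2. Apply the Aim 2 comparison to each separately. Report the infant result as an estimate with a confidence interval that allows for clustering, beside timely infant diagnosis, and state that its denominator depends on testing.
3. State for Survival, Retention in care, Non-adherence and Virological suppression whether the unit is the woman, the infant or both. Where both are meant, report them separately.

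The first two changes cost one extra row in Table 1 and in the results tables. The existing outcome already needs diagnosis and ART start dates for both groups, so no new data are collected. The price is a small and imprecise infant row. The third change is a matter of wording if Survival means the women. Adding infant survival in that case would be a new outcome, and infant vital status is not among the register items that Section III.C names.
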